## 5.2. Definition of dose-limiting toxicity:

For purposes of dose-escalation, dose-limiting toxicity (DLT) will be defined as the occurrence of any of the following during the first 28 days of therapy:

- ❖ Any grade 3 or 4 non-hematologic toxicity with the following exceptions:
  - Transient laboratory abnormalities that can be treated or resolve to grade 2 or less within 1 week from holding study drug.
  - Grade 3-4 non-hematologic toxicities that resolve to  $\leq$  Grade 1 within 1 week of holding study drug
  - Grade 3-4 expected and known drug class-related toxicities associated with differentiation syndrome (see definition below in section 9.2.4) that resolve within 2 weeks of steroid therapy to grade 1 will be excluded as DLT for purposes of dose escalation. This is due to the fact that such events are expected of therapy with retinoids that are effectively causing differentiation. If grade 3 or above differentiation syndrome recurs after this time, it will then be considered a DLT.
  - Asymptomatic Grade 3 hypertriglyceridemia will not be considered a DLT for purposes of dose escalation.
- ❖ Grade 4 hematologic toxicity, including only *treatment-associated* aplasia (to be investigated with a BM test) that persists beyond 4 weeks. Given that severe anemia, neutropenia and thrombocytopenia are features of AML and are commonly encountered in this patient population, they will not be used to define DLT except if associated with prolonged treatment-associated aplasia.
  - If the bone marrow at the end of cycle 1 or 2 of therapy is hypoplastic, as defined by less than 5% cellularity, the patient may have a drug-free window of up to 2 weeks to look for count recovery and treatment will be re-initiated after this time if toxicity returns to  $\leq$  Grade 3

Management and dose modifications associated with the above adverse events are outlined in Section 6.

Toxicities will be assessed during the first cycle of therapy and throughout the trial to make sure there are no late adverse effects. If any chronic toxicity becomes apparent, we will evaluate whether changes in trial design are required.

Dose escalation will proceed within each cohort according to the following scheme.

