### 5.3.3. Hypertriglyceridemia

Per the FDA drug label for the similar agent Tretinoin, “up to 60% of patients experienced hypercholesterolemia and/or hypertriglyceridemia, which were reversible upon completion of treatment. The clinical consequences of temporary elevation of triglycerides and cholesterol are unknown, but venous thrombosis and myocardial infarction have been reported in patients who ordinarily are at low risk for such complications.” In attempt to prevent such complications, patients who develop the known drug-class side effect of hypertriglyceridemia grade 3-4 (>500 mg/dL) should be treated with gemfibrozil 600 mg orally twice daily, given 30 minutes before morning and evening meals. IRX5183 should be held in the setting of grade 4 (>1000 mg/dL) hypertriglyceridemia until resolution to grade 3 or less, while on concomitant gemfibrozil. Lovaza (omega-3-acid) 4 grams orally divided qday to bid with meals may be considered on a case-by-case basis in consultation with the PI. Grade 3-4 elevations associated with clinical symptoms, such as pancreatitis, will result in permanent discontinuation of IRX5183.

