### 5.4. Duration of therapy:

Treatment is planned for 56 days of induction therapy (as above) and four 28-day cycles of consolidation/maintenance in patients with at least SD after induction, with an opportunity to continue on maintenance if patients remain in at least SD after 4 cycles of consolidation/maintenance (see details in section 5.1 above), or until one of the following criteria applies:

- 1) Disease progression as defined in IWG-2003 (**Appendix A1**) for AML and IWG-2006 for MDS (**Appendix A2**).
- 2) Intercurrent illness that prevents further administration of treatment or inability of the patient to continue treatment for any other reason.
- 3) Unacceptable adverse event(s) requiring temporary or permanent stopping of study drug defined in sections 5.2 and 6.
- 4) Patient decides to withdraw from the study.
- 5) General or specific changes in the patient's condition render the patient unacceptable for further treatment in the judgment of the investigator.
- 6) Pregnancy  
All WOCBP should be instructed to contact the investigator immediately if they suspect they might be pregnant (e.g., missed or late menstrual period) at any time during study participation. Institutional policy and local regulations should determine the frequency of on study pregnancy tests for WOCBP enrolled in the study.

The investigator must immediately notify Io Therapeutics in the event of a confirmed pregnancy in a patient participating in the study or partner of the patient.

7) Termination of the study by sponsor.

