### 5.6. **Criteria for removal from study:**

Patients will be removed from study when any of the criteria listed in Sections 3.5, 5.2, and 5.4 applies. The reason for study removal and the date the patient was removed will be documented in the Case Report Form.

Some patients may have improvement in their baseline PB counts, including a decrease in peripheral blasts following the start of IRX5183 dosing. It is also possible that peripheral counts will worsen or the number of BM blasts will increase with the initiation of therapy. In some cases, patients will not have had sufficient time to develop the required amount of differentiation to impact the counts. It is also possible that increases in blasts or other disease parameters may represent differentiation of leukemia cells in response to IRX5183. In conventional studies, such changes may be worrisome for PD and lead to the premature discontinuation of study drug. Patients with minor blast increases (defined as an increase of  $\leq 50\%$  of baseline bone marrow blast count) or worsening PB counts *prior to* week 8 may continue on study provided that they remain stable clinically. Primary tumor assessments will be made using IWG 2003 and IWG 2006 criteria at the completion of induction therapy (**Appendix A1-A3**).

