### 6.1. Dose Modifications for IRX5183:

Decisions to hold or discontinue a specific IRX5183 dose will be made on safety criteria. Treatment with IRX5183 will be skipped or discontinued if the subject experiences at least one adverse event, specified below, considered by the investigator to be “possibly,” “probably,” or “definitely” related to IRX5183 treatment.

Any adverse event that will prompt a skipped dose or discontinuation of IRX5183 must be reported. The investigator should contact the study PI to discuss any questions.

The following criteria will be used to determine dose skipping, restarting doses, or discontinuing IRX5183 during the trial:

It is necessary to avoid study drug dosing and initiate appropriate evaluation and/or treatment for the following adverse events:

Any  $\geq$  grade 3 skin related adverse event regardless of causality.

Any  $\geq$  grade 2 non-skin related adverse event, except for easily correctable laboratory abnormalities that do not reflect underlying organ pathology.

Any  $\geq$  grade 3 laboratory abnormality, aside from cytopenias.

Any adverse event, laboratory abnormality or intercurrent illness that, in the judgment of the investigator, presents a substantial clinical risk to the subject with continued dosing.

It may be necessary to hold study drug to evaluate Grade 1 events that suggest ongoing or incipient differentiation syndrome, including unexplained fever, dyspnea, renal failure, hypotension, and/or unexplained weight gain until diagnosis is determined.

IRX5183 may be restarted if/when the adverse event(s) resolve(s) or returns to baseline or  $\leq$  grade 1 within 2 weeks:

If the adverse event has been determined not to be related to IRX5183: If  $>1$  dose is to be skipped or  $> 1$  week delay is expected due to current events not related to the study, the dosing schedule modifications must be discussed with the principal investigator prior to implementation.

If the adverse event has resolved to  $\leq$  grade 1, IRX5183 dosing may be restarted where the patient left off in their cycle of therapy.

The following criteria will be used to determine dose skipping, restarting doses, or discontinuing IRX5183 during *phase II* of the trial:

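### Sections 5.3.3, 6.1 and 6.2 give contradictory hold, restart and stopping rules for triglycerides, and the first DLT exception in 5.2 is ambiguous for treatable laboratory abnormalities

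*Combined protocol and SAP*

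**What the plan says.** **DLT definition (5.2).** Any grade 3 or 4 non-hematologic toxicity in the first 28 days is a DLT, with four exceptions.

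- The first covers "Transient laboratory abnormalities that can be treated or resolve to grade 2 or less within 1 week from holding study drug".
- The second covers "Grade 3-4 non-hematologic toxicities that resolve to" grade 1 or less within a week of holding drug.
- The third concerns differentiation syndrome.
- The fourth reads "Asymptomatic Grade 3 hypertriglyceridemia will not be considered a DLT for purposes of dose escalation".

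**Triglyceride management (5.3.3).** On treatment, "hypertriglyceridemia grade 3-4 (>500 mg/dL) should be treated with gemfibrozil 600 mg orally twice daily". On holding, "IRX5183 should be held in the setting of grade 4 (>1000 mg/dL) hypertriglyceridemia until resolution to grade 3 or less". Symptomatic grade 3-4 elevations end treatment for good.

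**General dose rules (6.1 and 6.2).** Section 6.1 tells sites to avoid dosing for any "grade 3 laboratory abnormality, aside from cytopenias" (that grade or higher). Restart is at baseline or grade 1 or less, within 2 weeks. Section 6.2 item 2 stops drug permanently for any grade 3 or 4 event, subject to exceptions in 5.2 and 6.1.

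**Removal (5.4 and 5.6).** Section 5.6 states "Patients will be removed from study when any of the criteria listed in Sections 3.5, 5.2, and 5.4 applies". Section 5.4 item 3 lists "Unacceptable adverse event(s) requiring temporary or permanent stopping of study drug defined in sections 5.2 and 6".

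**The concern.** Raised triglycerides are an expected class effect. Section 2.5 says IRX5183 retains it, and 9.2.1 reports hypertriglyceridemia in 20% of the earlier phase I patients, without grades. The protocol should therefore give one answer to each of three questions: when to hold, when to restart, and when the event is a DLT. It does not.

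Two things are at stake. The first is dosing safety: two sections instruct the site differently for the same grade 3 value. The second is escalation: determining DLTs is part of the phase I primary endpoint, and DLT counts drive Table 2. A treatable grade 4 laboratory event can be read as exempt or as counting, and with six patients at a level one event can change the decision.

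**Working it through.** The plan states no figure on this point to reproduce. The check sets the rules side by side, then follows one case through them.

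**Step 1. Hold and restart rules**

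| Asymptomatic triglycerides | 5.3.3 | 6.1 | 6.2 item 2 |
|---|---|---|---|
| Grade 3 (above 500, up to 1000 mg/dL) | gemfibrozil, no hold | avoid dosing | exempt through 5.2 |
| Grade 4 (above 1000 mg/dL) | gemfibrozil and hold | avoid dosing | permanent stop unless a 5.2 or 6.1 exception applies |
| Restart | grade 3 or less, no deadline | baseline or grade 1 or less within 2 weeks | none |

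Sections 5.3.3 and 6.1 disagree on both the hold grade and the restart grade, however 5.2 is read. The carve-out in 6.1 for readily corrected laboratory findings is attached to its grade 2 adverse-event line, not to its grade 3 laboratory line. Section 5.2 sends management of the events it lists to Section 6. Section 6 points back to 5.3.1 for differentiation syndrome but has no matching pointer to 5.3.3.

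**Step 2. Two readings of the first exception**

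- Broad: a transient abnormality is exempt if it can be treated, or if it falls to grade 2 or less within a week. The treatable branch has no grade or deadline beyond being transient.
- Narrow: treated or not, the value must reach grade 2 or less within a week.

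The narrow reading is favoured. Section 5.3.3 gives gemfibrozil for every grade 3-4 value, so on the broad reading the separate exemption for asymptomatic grade 3 triglycerides would be largely redundant.

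**Step 3. The disputed case**

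Take asymptomatic grade 4 triglycerides in the first 28 days that fall to grade 3, but not to grade 2 or less, within a week of the hold.

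- Narrow reading: the first exception needs grade 2, the second needs grade 1, the third is not relevant and the fourth covers grade 3 only. The event is a DLT. Section 5.6 removes the patient; 5.3.3 lets dosing resume.
- Broad reading: if transient and treatable, the event is exempt, is not counted, and raises no conflict with 5.6.

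If the value reaches grade 2 or less within the week, it is not a DLT on either reading.

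**Step 4. Effect on Table 2, with no rate assumed**

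Six patients at a level, one with an undisputed DLT and one with the disputed event:

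- Not counted: 1/6 = 16.7%.
- Counted: 2/6 = 33.3%, so the level becomes the maximally administered dose (MAD).

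At DL1 the next dose is 75 mg or 25 mg. At DL3 the RP2D is 100 mg or 75 mg, the latter if DL2 has fewer than 2 of 6. In a first cohort at DL1 or DL2, 0/3 means escalate and 1/3 means three more patients.

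**Step 5. Illustrations on assumed rates**

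*Conditional.* One disputed patient is among the first three at DL1 or DL2 and has no other DLT. The other two, and any three added, each have an assumed DLT rate p.

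- Not counted: P(MAD) = p² + 2p(1−p)[1 − (1−p)³]
- Counted: P(MAD) = 1 − (1−p)⁵

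At p = 0.10, not counted: 0.01 + 0.18 × 0.271 = 0.059. Counted: 1 − 0.590 = 0.410.

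| p | Not counted | Counted |
|---|---|---|
| 0.10 | 5.9% | 41.0% |
| 0.15 | 12.1% | 55.6% |
| 0.20 | 19.6% | 67.2% |

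*Unconditional.* Assume a 10% risk of other DLTs and an independent risk q of a treatable laboratory event that misses grade 2 within a week. With total risk t, P(escalate) = (1−t)³ + 3t(1−t)²(1−t)³. If the event never counts, t = 0.10. If it counts, t = 1 − 0.9(1−q).

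| q | P(escalate), not counted | P(escalate), counted |
|---|---|---|
| 2% | 0.906 | 0.875 |
| 5% | 0.906 | 0.824 |
| 10% | 0.906 | 0.730 |
| 20% | 0.906 | 0.536 |

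**Step 6. Can the 1-week test be applied?** Lipids are scheduled every 2 weeks in the first month (7.2 and the Section 10 calendar). After a grade 4 value at week 2, the next scheduled panel is about 14 days away. Extra draws are allowed but none is required at day 7.

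**The case against.** The strongest reply is that a sensible site would manage. Section 5.3.3 is the only triglyceride-specific rule and is naturally taken to override a general one. The trial is single-center, and 6.1 sends questions to the PI. The RP2D rule is hedged and follows review of all clinical data. If the narrow reading is right, the DLT count is determinate. DLTs are defined for dose escalation, so a DLT removal can be read as overriding 5.3.3 for that patient. Nor can the removal text be taken wholly literally: 5.4 item 3 includes temporary stops, so every hold would mean removal, contrary to the restart rules.

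The event may also be rare. Section 2.5 reports no triglyceride DLT among 15 patients at 15 to 60 mg/m² and no DLT among 8 at 60 mg/m². Since 5.1 equates 50 mg with about 30 mg/m², 100 mg is about 60 mg/m².

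Much of this stands as a limit on size. The earlier trials suggest rarity but do not prove it, because their DLT definitions are not given. The specific-over-general argument is reasonable, but no text adopts it, and the pointer from 5.2 leads to Section 6. Review of all data informs the RP2D; it does not settle how a cohort is counted. That the removal text needs interpretation is itself a reason to clarify it.

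**Conclusion.** The point holds in two parts. First, 5.3.3 and 6.1 cannot both be followed for grade 3 triglycerides, whichever reading of 5.2 is taken. Section 6.2 item 2 adds to this by omitting 5.3.3 from its exceptions; its reach at grade 4 depends on how 5.2 is read. Second, the first DLT exception is ambiguous, and one patient of the kind described can turn 1/6 into 2/6.

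A reader might infer more than the documents support:

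- *That 5.2 plainly sets no grade or time limit on treatable laboratory abnormalities.* This is true only on the broad reading, which the triglyceride exception counts against.
- *That 5.6 removes every patient with grade 4 triglycerides.* Through the DLT route it reaches only asymptomatic patients, in the first 28 days, who fall to grade 3 but not grade 2 within a week, and only on the narrow reading.
- *That an uncounted event and a removal conflict occur together.* They belong to different readings. The uncertainty in the count comes from not knowing which reading will be used.
- *That 41.0% to 67.2% is a chance of stopping wrongly.* Those figures presuppose a disputed patient and assume p. They say nothing about how often such a patient occurs, which is not documented.

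This is a problem of wording and cross-references, but it bears on dosing safety and on the escalation decision. It should be corrected.

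**What to change.** 1. Reword the first exception in 5.2 to: *laboratory abnormalities that resolve to grade 2 or less within 1 week, with treatment and/or holding study drug*. Asymptomatic grade 4 hypertriglyceridemia in the first 28 days is then a DLT unless it meets that test.
2. State that 5.3.3 governs triglyceride holds and restarts in place of the general laboratory rule in 6.1, and name it as an exception to 6.2 item 2. Where the event is a DLT under 5.2, 5.6 applies instead.
3. Require a fasting triglyceride recheck within 7 days of a grade 4 hold, at an already scheduled visit. For a week 4 panel drawn on day 22, this is the cycle 2 day 1 visit on day 29.

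The cost is amendment wording and one extra lipid panel for affected patients only. The downside is that slightly more events may count as DLTs. The sponsor should accept that knowingly, since item 1 settles the DLT status of grade 4 triglycerides.

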### **Study Phase I:**

In the dose-escalation part of the study, we will abide by a traditional 3+3 design with 3 dose levels (dose level 1 [DL1] with 50 mg IRX5183, DL2 with 75 mg, and DL3 with 100 mg), with 1 additional dose level, DL(-1), to be only used if excessive toxicity is noted at the DL1. There will be no intra-patient dose escalation.

The first patient will enter the trial on DL1. The dose for level 1 will be a flat dose of 50 mg IRX5183 daily per the schedule above. We will enroll 3 patients at a time to determine the toxicity profile of IRX5183. If none of the 3 patients receiving DL1 experiences a DLT, another 3 patients will be treated at the next higher dose level. However, if 1 of the first 3 patients experiences a DLT, 3 more patients will be treated at the same dose level. The dose escalation will continue until at least 2 patients among a cohort of 3 to 6 patients experiences DLTs. If 2 or more patients experience a DLT on DL1, the next patient will be recruited to DL(-1). The RP2D of single agent IRX5183 will generally be the highest dose at which the DLT rate is <33% in at least six patients. If no MTD is determined, the highest dose

[figure not shown]
explored will be 100 mg. At the end of phase I, the RP2D will be determined after careful review of all of the clinical data available. The first 3 subjects enrolled to any cohort must have passed the 28 day DLT evaluation point before the 4th subject will begin treatment.

IRX5183 will be initiated at the company’s currently recommended dosage for use in APL patients of 50 mg daily (about 30 mg/m^2/day). The drug is available in 25 mg capsules, so we will be using a flat dosage. This dose of 50 mg is above the MTD of 15 mg/m^2/day from the prior phase I trial conducted in solid tumor patients. However, the DLTs seen in this trial were elevations in alkaline phosphatase in patients with known liver metastases. In addition, the phase I/II trial in patients with myeloma and lymphoma used a dose of 60 mg/m^2, which was well tolerated with no serious adverse events (SAEs). The roughly 2 months of induction therapy followed by consolidation/maintenance described above is modeled after prior studies of ATRA and other synthetic retinoids, in which it can take up to 60 days to see an initial response (Lo-Coco et al., 2013; Sanford D, 2014; Tobita et al., 1997).

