**Table 2: Dose escalation rules.**

Number of Patients with DLT at a Given Dose Level (DL)	Escalation Decision Rule
0 out of 3 in DL1	Enter 3 patients at the next dose level (DL2). If DL2 the maximally administered dose (MAD), enroll 3 more pts at DL1 and if $< 2$ of 6 have DLT, DL1 will be the RP2D
1 out of 3 in DL1	Enter 3 additional patients at DL1 and if $< 2$ of 6 have a DLT,

	enter 3 patients at the next dose level (DL2)
≥ 2 out of 6 in DL1	Dose escalation will be stopped. DL1 will be declared the MAD, and DL(-1) will be the RP2D if < 2 of 6 had a DLT at that level
0 out of 3 in DL2	Enter 3 patients at the next dose level (DL3). If DL3 the MAD, enroll 3 more pts at DL2 and if < 2 of 6 have DLT, DL2 will be the RP2D
1 out of 3 in DL2	Enter 3 additional patients at DL2 and if < 2 of 6 have a DLT, enter 3 patients at the next dose level (DL3)
≥ 2 out of 6 in DL2	Dose escalation will be stopped. DL2 will be declared the MAD, and DL1 will be the RP2D if < 2 of 6 had a DLT at that level
0 out of 3 in DL3	Enter an additional 3 patients at DL3 and if < 2 of 6 have a DLT, DL3 will be the RP2D
1 out of 3 in DL3	Enter an additional 3 patients at DL3 and if < 2 of 6 have a DLT, DL3 will be the RP2D
≥ 2 out of 6 in DL3	DL3 will be declared the MAD, and DL2 will be the RP2D if < 2 of 6 had a DLT at that level

Note: DL(-1) will be only used if maximally administered dose reached at DL1. If DL(-1) is used and DLT occurred in < 2 of 6 patients, then DL(-1) will be used as the recommended phase 2 dose. If ≥ 2 out of 6 patients in DL(-1) have DLT, then the study will be terminated.

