### 7.2. Assessment of Response:

1. Complete blood counts with WBC differential will be measured twice weekly during the first cycle of treatment, at least weekly throughout the second cycle of therapy, at least every other week during consolidation/maintenance, and at least monthly during extended maintenance, or as often as clinically indicated.
2. Blood chemistries will be measured twice weekly during the first cycle of treatment, at least weekly throughout the second cycle of therapy, at least every other week during consolidation/maintenance, and at least monthly during extended maintenance, or as often as clinically indicated.
3. Fasting lipids with triglyceride evaluation will occur q2 weeks through the first month and then q8 weeks subsequently for assessment of toxicity.
4. Bone marrow aspirate and biopsies for clinical assessment (morphologic analysis, cell count/differential, flow cytometry, FISH/cytogenetics for patients with baseline abnormalities, and molecular studies for patients with baseline abnormalities) and biologic correlates (see section 8 below) will be collected at the following time points:
  - ❖ Day 14 ( $\pm$  3 days) of cycle 1 (not required to stay on study)
  - ❖ At the completion of cycle 1
  - ❖ At the completion of cycle 2
  - ❖ At the end of every two cycles of treatment during consolidation/maintenance
  - ❖ After every 4 cycles of treatment during extended maintenance
  - ❖ Drug levels will be obtained in the peripheral blood (PB) and BM with liquid chromatography mass spectroscopy (LCMS), described in detail in section 7.8.
5. PT/PTT will be followed as needed for those patients who are receiving an anticoagulant during protocol therapy.
6. A track of the total number of transfusions required will be kept.
7. Quality of life assessment per the FACTLeu questionnaire (available at <http://www.facit.org/FACITOrg/Questionnaires>) at the completion of the induction and maintenance phases, with the help of the research team.
8. Response to treatment will be assessed after completion of at least 2 cycles. Patients will be categorized based on standard IWG-2003 response criteria for AML (Appendix A1) and IWG-2006 criteria for MDS (Appendix A2-A3) and patients with at least SD will continue on treatment (see section 5.1).
9. All patients will be evaluated for hematologic improvement (HI) per IWG-2006 MDS criteria (Appendix A2).

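### The only hematologic DLT, aplasia beyond 4 weeks, cannot be met before day 29, but section 5.2 stops counting DLTs, and section 5.1 opens enrolment, at day 28

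*Combined protocol and SAP*

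**What the plan says.** Section 5.2 defines a DLT as the "occurrence of any of the following during the first 28 days of therapy". Under Study Phase I in section 5.1, the enrolment gate is: "The first 3 subjects enrolled to any cohort must have passed the 28 day DLT evaluation point before the" 4th subject starts treatment. In Table 2, the action after 0 of 3 DLTs at DL1 is "Enter 3 patients at the next dose level (DL2").

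Several section 5.2 criteria carry a clock of their own:

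- **Hematologic.** Grade 4 toxicity counts only as treatment-associated aplasia, "to be investigated with a BM test) that persists beyond 4 weeks". Other cytopenias are set aside because the disease itself causes them. If the marrow after cycle 1 or 2 is hypoplastic, "the patient may have a drug-free window of up to 2 weeks to look for count recovery".
- **Differentiation syndrome.** Grade 3-4 toxicities of the syndrome "that resolve within 2 weeks of steroid therapy to grade 1 will be excluded as DLT for purposes of dose escalation". Sections 5.3.1 and 6.1 say that failure to reach grade 1 in that time makes the event a DLT.
- **One-week exceptions.** One covers "Transient laboratory abnormalities that can be treated or resolve to grade 2 or less within 1 week from holding study drug". Another covers grade 3-4 non-hematologic toxicities that fall to grade 1 or less within a week of holding drug.

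On marrow timing, section 7.2 lists the day 14 sample "of cycle 1 (not required to stay on study"). The next marrow is at the completion of cycle 1.

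**The concern.** A 3+3 decision needs every patient in the cohort classified as DLT or no DLT when it is taken. Here the counting window and the enrolment gate both sit at day 28, while one criterion needs more than 28 days of persistence and others allow 1 or 2 weeks for resolution. Nothing in section 5.1 or Table 2 says how to count a patient whose classification is pending at day 28, whether enrolment waits, or whether a DLT confirmed later reverses a step already taken.

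At stake is the Table 2 action. One more DLT turns 0 of 3 (escalate) into 1 of 3 (treat 3 more at the same dose). It also turns 1 of 6 (the dose passes) into 2 of 6 (the dose is the maximally administered dose). The problem is sharpest for aplasia, because it is the only route by which hematologic toxicity can stop escalation.

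**Working it through.** There is no computed figure to reproduce; the 28 days is a design rule. The check is calendar arithmetic on the plan's own rules, with day 1 as the first dose.

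**Inputs.** Window and gate: 28 days (5.2, 5.1). Aplasia: more than 28 days (5.2). Post-cycle recovery window: up to 14 days (5.2). Syndrome allowance: 14 days of steroids (5.2), which 5.3.1 says to start immediately. One-week exceptions: 7 days from holding drug (5.2).

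**Aplasia.** With onset on day d, the first day beyond 4 weeks is d + 28.

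- Onset on day 1: 1 + 28 = day 29.
- Onset on day 28: 28 + 28 = day 56.
- The condition d + 28 > 28 holds for all 28 possible onset days.
- If the 4 weeks run from the start of therapy instead, the earliest day is again 29.

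The marrow schedule points the same way. With day 14 optional, the only required cycle 1 marrow is at about day 28, and the recovery window then runs to 28 + 14 = day 42.

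The two readings of section 5.2 give:

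| Reading | Does aplasia count as a DLT? | Known when the gate opens? |
|---|---|---|
| The whole criterion must be met within 28 days | Never | Not applicable |
| Onset within 28 days is enough | Yes, confirmed on days 29-56 | No |

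**Differentiation syndrome (secondary).** Steroids started on day d have their allowance end on d + 14. This exceeds 28 for d = 15 to 28, which is 14 of 28 days, and the end falls on days 29-42.

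**One-week exceptions (secondary).** Drug held on day d has its allowance end on d + 7. This exceeds 28 for d = 22 to 28, which is 7 of 28 days, and the end falls on days 29-35.

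These are counts of calendar days for a case that uses its full allowance. They are not probabilities, and a case that resolves by day 28 is not open.

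**Sensitivity to the meaning of days of therapy.** If a hold of h days does not count as therapy, the window closes on calendar day 28 + h.

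- Syndrome: d + 14 > 28 + h leaves 11, 7 or 0 of 28 days for h = 3, 7 or 14.
- Aplasia: it fits inside the window only if d + 28 ≤ 28 + h, that is, onset by day h of a cycle that happened to include such a hold. Sections 6 and 6.1 do not use neutrophil changes or cytopenias to hold drug, so aplasia would not usually create that hold itself.

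**The case against.** The strongest reply concerns the non-hematologic cases. Section 5.2 first makes any grade 3-4 non-hematologic toxicity a DLT and then removes only those that resolve in time. A case still open at day 28 has not earned its exception, so on the most literal reading it is a DLT until it does. Section 5.3.1 refers back to that rule. A reader might infer that the plan, followed to the letter, escalates past a patient still on steroids for unresolved grade 3-4 syndrome. The documents do not support that: it needs the less literal reading, and escalation also requires that none of the 3 patients has had a DLT. What survives is an ambiguity. Sections 5.3.1 and 6.1 describe the event as becoming a DLT after 2 weeks without resolution, and neither the gate nor Table 2 says which reading applies. The laboratory exception is looser still: an abnormality that can be treated may not need the full week to classify.

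On aplasia, the reply is that occurrence means onset, with persistence as the severity that must follow; the recovery window shows the plan expects follow-up after day 28. This rescues the definition but not the gate, which still opens before the answer is known. The default that helps open syndrome cases does not help here, because persistence is part of the definition.

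The gate is a minimum, so investigators may wait, but nothing requires it. Toxicity is followed throughout the trial, and all clinical data are reviewed before the RP2D is set. Those safeguards limit the harm to the final dose choice, but the RP2D review comes at the end of phase I, after patients could have been treated at the next level.

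**Conclusion.** The point holds for aplasia: the only hematologic DLT cannot be established by the day on which the plan counts DLTs and opens enrolment. Literally it never counts; dated by onset, it is unclassified at the gate for all 28 onset days. For the syndrome and the 1-week exceptions the point is secondary. Cases can be open until day 42 and day 35, section 5.2 is best read as counting them meanwhile, and the plan should say so.

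This rests on calendar days from first dose and on steroids starting at onset. No statement is made about how often a decision would change. The documents give no rate for the syndrome or aplasia with this drug in these patients. The syndrome is described as expected with effective retinoids (5.2) but also as something that may not be seen (11.7), and anemia is the only hematologic event listed from the earlier phase I trial (9.2.1). A reader might turn the day counts into a risk of wrong escalation; the documents do not support that step. The phase II sample size is unaffected. A change is still warranted, because a stated safety rule does not work as written and the repair is short.

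**What to change.** In section 5.2, date a DLT by onset of the toxicity within the first 28 days. Count it if it later fails its resolution exception or, for aplasia, persists beyond 4 weeks, even when that is established after day 28. State whether the 4 weeks run from onset or from the start of therapy, and whether held days count.

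In section 5.1, and by reference in Table 2, start no further subject in the cohort and no next dose level until open cases are classified. If a decision is taken earlier, count an open non-hematologic case as a DLT. This should also cover subjects 4 to 6, since the present gate names only the first 3.

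The cost is a short wording amendment; waiting needs no new patients or tests. Delay arises only in cohorts with an open case: up to 7 days for the 1-week exceptions (35 − 28), up to 14 days for the syndrome (42 − 28), and up to about 4 weeks for late-onset aplasia (56 − 28). Counting an open non-hematologic case as a DLT avoids the wait but can add a 3-patient expansion for a case that later resolves.
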